3.1 Investigator Training

Training sessions in proper surgical technique and trial performance for the Principal Investigator, all Sub-Investigators and research coordinators will be provided by the sponsor prior to initiation of the study at each site.

4 STUDY METHODS

4.1 Study Design

Prospective, non-randomized (single arm) multi-center study to evaluate the perioperative and post-operative radiographic and patient outcome variables of the VESUVIUS Demineralized Fibers and the EVEREST Spinal System compared to literature reported outcomes for traditional autograft and posterior stabilization treatment of spinal stenosis, spondylolisthesis, and/or degenerative disc disease (DDD).

4.2 Treatment Group

Patients treated with the VESUVIUS Demineralized Fibers and EVEREST system that had/were:

- Diagnosis of spinal stenosis, spondylolisthesis (grade 1 or 2), and/or degenerative disc disease (DDD). Qualified patients will be confirmed for inclusion by patient history and radiographic studies.
- One or two contiguous levels requiring surgical intervention between L1-S1
- Skeletally mature and ≥ 18 years old at time of enrollment

4.3 Control Group – Comparative Data

Literature reported outcomes of adult patients (≥ 18 years old) with surgical intervention utilizing autograft and posterior stabilization for the treatment of spinal stenosis, spondylolisthesis and/or DDD.

4.4 Sample Size

Two-hundred four (204) total subjects at up to 15 clinical sites, geographically distributed throughout the US. Sites are considered a Principal Investigator and their Sub-Investigators who function under the same institution and/or are covered by a single Institutional Review Board's (IRB's) oversight and approval.

Subject enrollment will be capped so that no single site contributes more than approximately 15% of the cases.

5 STUDY OBJECTIVES/OUTCOMES

5.1 Primary Study Objective

The primary study objective is:

5.1.1 Radiographic Assessment of Fusion

Radiographic assessments by CT scan at the 12 month visit and AP, lateral, Flex/Ext and oblique x-rays at the 12 and 24 month visits include overall assessment of fusion. Fusion will be graded by an independent radiologist taking into account signs such as:

- Bony Bridging
- Radiolucency
- Development of Pseudoarthrosis

5.2 Primary Safety Objectives

The primary safety objectives are:

- The evaluation of all adverse events including device related, procedure related and additional serious adverse events.
- Additional surgical intervention at the operative site including supplemental fixation, revision and/or device removal

All adverse events will be documented on a continuous basis and reviewed by K2M Clinical Research Staff. Information regarding all device failures including implant breakage, subsidence, migration, or expulsion will be captured.

5.2.1 Device and Procedure Adverse Events

Device and procedure adverse events will be documented and reported to the sponsor, including the need for removals, revisions, re-operations or supplemental fixation required to modify the device.

5.3 Secondary Objectives

Secondary objectives are expected to further define the safety and patient outcomes for effectiveness of the K2M device. Secondary objectives include:

5.3.1 Oswestry Disability Index

The Oswestry Disability Index (ODI) is one of the principal condition-specific outcome measures used in the management of spinal disorders. The ODI is the most commonly used outcome measure in patients with low back pain. It has been extensively tested, showed good psychometric properties, and applicable in a wide variety of settings. This patient-reported outcome measure is a 10 item questionnaire that evaluates disability and functional impairment associated with back problems. This validated instrument includes items that relate to subjective symptomatology and activities of daily living (pain intensity, personal care, lifting, walking, sitting, standing, sex life, traveling). Each item is scored from 0 up to 5, with higher scores corresponding to greater disability. A total ODI score is determined by adding the scores of the individual questions and dividing that total by the maximum possible score (i.e., 50 if all questions are answered) to yield a percentage. Therefore, the ODI score ranges from 0% to 100%.

5.3.2 Visual Analog Scale

The severity of back, hip/buttock, and leg pain will each be evaluated in all study subjects using a 10-cm visual analog scale (VAS). The study will employ a 15% improvement for success.

5.3.3 *Health-Related Quality of Life*

Health-related quality of life will be evaluated in all study subjects using the SF-12v2 Health Survey. This shortened and simplified version of the SF-36 makes the questionnaire less ambiguous for patients. It has a self-administered form that makes it easy to read and complete, and that reduces missing responses. The physical and mental component summary scales, referred to as PCS-12 and MCS-12 will be evaluated against published normative values and a 15% improvement in these scores will be used as an assessment of success.

5.3.4 *Radiographic Assessments*

Qualitative radiographic assessment of the post-operative AP, lateral and oblique images will be performed by an independent radiologist. Radiographic assessments being performed include, but are not limited to:

- Posterior/Transverse process fusion, Right side (by level)
- Posterior/Transverse process fusion, Left side (by level)
- Anterior fusion, if TLIF procedure done, by level
- Overall fusion by level
- Device Condition
- Device Subsidence
- Device Migration

5.3.5 *Patient Satisfaction*

At the 12 month and 24 month follow-up visits, subjects will be asked whether they were satisfied with the outcome of their surgery (Yes/No) and whether they would repeat the operation (Yes/No).

5.3.6 *Surgery Time*

The length of the surgical procedure from the initial incision to final closure will be captured from the Anesthesia Record.

5.3.7 *Anesthesia Time*

The length of time the patient is under anesthesia will be captured from the Anesthesia Record.

5.3.8 *Estimated Blood Loss*

The amount of blood loss over the entire length of the surgery, documented on the Anesthesia Record will be captured.

5.3.9 *Length of Hospital Stay*

The length of hospital stay from the date of admission to the date of discharge will be calculated.

5.3.10 *Functional and Economic Status and Return to Work/School*

The subject's economic and functional status as well as ability to and the time it takes for the subject to be cleared to return to work/school, as judged by the Investigator, from the date of surgery will be documented. Economic and functional status will be assessed using the Prolo Scale as modified by Voorhies in 2007.¹

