7.3 Study Duration

Study subjects will be expected to participate in this study for 24 months following surgery, with follow-up evaluations at initial post-op, 3 months, 6 months, 12 months, and 24 months.

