8.4.1 Follow-Up Evaluation Data – Post-op through 24 Months

- Functional, Economic and Work/school Status (including release for return to work/school) (initial post-op, 3 month, 6 month, 12 month, and 24 month)
- Current Symptoms (all visits)
- Medication (taken for spine problem since last contact) (initial post-op, 3 month, 6 month, 12 month, and 24 month)
- Neurological Examination (initial post-op, 3 month, 6 month, 12 month, and 24 month)
- AP, Lateral, Oblique and Flex/Ext x-rays (6 month, 12 month, and 24 month)
- Oswestry Disability Index (initial post-op, 3 month, 6 month, 12 month, and 24 month)
- Back, Hip/Buttock, and Leg VAS (initial post-op, 3 month, 6 month, 12 month, and 24 month)
- SF-12v2 (initial post-op, 3 month, 6 month, 12 month, and 24 month)
- Adverse Event Assessment (all visits)
- CT Scan (12 month)
- Patient Satisfaction (12 month, 24 month)
- Study Exit

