12.7 Supplementary Analysis

Other ancillary variables such as demographics, baseline variables, surgical variables and post-op pain medication usage will be summarized by mean, standard deviation, median (if appropriate), and range for continuous measures, and frequency and percent for categorical measures. Descriptive statistics and graphical methods such as bar graphs, box and whiskers plots, and star plots may be employed to compare subjects' clinical outcomes to baseline values (pre-operative) and the prospective and historical study groups simultaneously for multiple variables.

Descriptive statistics or graphical methods will also be used to explore the impact of any covariates of interest, e.g., presence or absence of anterior spacer on the prospectively collected outcome data.

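### Time to clearance for work or school is right-censored, but section 12 gives no time-to-event method, and the default summary in 12.7 would use cleared subjects only and understate the time

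*Combined protocol and SAP*

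**What the plan says.** Section 5.3.10 lists among the secondary objectives the subject's ability to return to work or school and "the time it takes for the subject to be cleared to return to work/school". The clock starts at surgery, clearance is the investigator's judgement, and the section promises only that the time will be recorded. It names no estimator and does not say how a subject without a clearance date is handled.

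Follow-up is finite: "Study subjects will be expected to participate in this study for 24 months following surgery" (7.3). Section 12.3 allows for 15% drop-out. Work/school status is taken pre-operatively (8.2.1). At the initial post-operative visit and at 3, 6, 12 and 24 months, section 8.4.1 collects "Functional, Economic and Work/school Status (including release for return to work/school".

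On analysis, 12.7 says that continuous measures "will be summarized by mean, standard deviation, median (if appropriate), and range for continuous measures" and that categorical measures get frequency and percent. The variables it covers are "Other ancillary variables such as demographics, baseline variables, surgical variables and post-op pain medication usage". That list is open, and return to work or school is not on it. For clinical outcomes, 12.7 adds that "Descriptive statistics and graphical methods such as bar graphs, box and whiskers plots, and star plots may be employed". Section 12 contains no time-to-event method, no censoring rule and no rule for missing values.

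**The concern.** A clearance time exists only for a subject who is cleared while under observation. A subject still uncleared at 24 months, or lost before clearance, is right-censored: the time is known only to exceed the time observed. A mean and SD cannot be computed for such a subject, so unless a rule is given the subject falls out of the summary. What remains is conditional on the good outcome, and it does not lengthen as more subjects fail to return.

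The eligibility criteria (7.2) do not require subjects to be working or studying before surgery. Retired or non-working subjects have no clearance to wait for, and the plan does not say whether they are in the denominator.

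The error runs one way, towards faster apparent recovery. The study has a single arm and is meant to be read against literature outcomes (1, 2.1), so no concurrent control carries the same bias and cancels it.

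**Working it through.** The documents give no figure for return to work or school, so there is nothing to reproduce. The check shows the direction of the effect and how its size depends on the unknown share never cleared.

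**Inputs from the documents.** Follow-up 24 months (7.3); drop-out 15% (12.3); N = 204 (12.3).

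**Assumptions not in the documents.** Drop-out spread evenly over 24 months; exponential clearance times with a 4-month median among subjects who would eventually be cleared; a share *q* never cleared of 0% to 30%.

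**Step 1: median over all subjects.** Half of all subjects are cleared when (1 − q)(1 − 2^(−t/4)) = 0.5, so t = 4 × log2[(1 − q)/(0.5 − q)].

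- q = 0: 4 × log2(2) = 4.0 months
- q = 0.10: 4 × log2(0.9/0.4) = 4.7 months
- q = 0.20: 4 × log2(0.8/0.3) = 5.7 months
- q = 0.30: 4 × log2(0.7/0.2) = 7.2 months

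**Step 2: median over cleared subjects only.** The chance of still being followed at month t is 1 − 0.15t/24 = 1 − 0.00625t. With λ = ln 2/4 = 0.1733, the share of eventual returners seen to be cleared by month t is

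F(t) = (1 − e^(−λt)) − 0.00625 × [(1 − e^(−λt))/λ − t e^(−λt)].

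F(24) = 0.984 − 0.033 = 0.951, half of which is 0.476. F(3.8) = 0.482 − 0.005 = 0.477, so the cleared-only median is about 3.8 months. The share q multiplies every term equally and cancels, so this median is the same at every q.

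**Step 3: subjects with no clearance time.** The share is 1 − 0.951(1 − q).

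| Never cleared | All-subject median (months) | Cleared-only median (months) | Understatement (months) | Subjects with no time |
|---|---|---|---|---|
| 0% | 4.0 | 3.8 | 0.2 | 5% |
| 10% | 4.7 | 3.8 | 0.9 | 14% |
| 20% | 5.7 | 3.8 | 1.9 | 24% |
| 30% | 7.2 | 3.8 | 3.4 | 33% |

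**Step 4: a different distribution.** 1,000 trials per row were simulated with 204 subjects at risk, the same drop-out and lognormal times (log SD 0.7). The median among eventual returners was set at 3 or 6 months. The last column is the true mean time not cleared, truncated at 24 months.

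| Median if cleared | Never cleared | Cleared-only median | Kaplan-Meier median | Cleared-only mean | True truncated mean |
|---|---|---|---|---|---|
| 3 | 0% | 2.97 | 3.00 | 3.74 | 3.83 |
| 3 | 10% | 2.96 | 3.30 | 3.75 | 5.83 |
| 3 | 20% | 2.97 | 3.76 | 3.74 | 7.84 |
| 3 | 30% | 2.97 | 4.44 | 3.74 | 9.85 |
| 3 | 40% | 2.98 | 5.97 | 3.74 | 11.93 |
| 6 | 0% | 5.78 | 5.99 | 6.93 | 7.46 |
| 6 | 10% | 5.77 | 6.62 | 6.94 | 9.14 |
| 6 | 20% | 5.79 | 7.52 | 6.94 | 10.77 |
| 6 | 30% | 5.80 | 8.98 | 6.93 | 12.45 |
| 6 | 40% | 5.80 | 11.73 | 6.94 | 14.07 |

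The pattern is the same: cleared-only summaries stay flat while the true time rises. At 20% never cleared, the median is low by 0.8 months (3.76 − 2.97) or 1.7 months (7.52 − 5.79), and the mean by about 4 months in both cases. At 0% the median is low by at most 0.2 months and the mean by at most 0.5. With 102 subjects at risk the results are nearly the same.

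**The case against.** The strongest reply is that this faults one way of carrying out the plan and not the plan itself. Section 12.7 does not name the outcome, and no text confines the summary to cleared subjects. A median that ranks uncleared subjects last would fit 12.7 and avoid most of the bias in the median. This stands as far as it goes: a reader might infer that the plan instructs analysts to discard uncleared subjects, and it does not. But if 12.7 does not govern this outcome, no analysis is specified for it. If 12.7 does govern, the mean and SD still have no value to use for an uncleared subject.

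Next, the uncleared need not be hidden. Ability to return is a recorded outcome, release is collected at every scheduled follow-up visit, and 12.7 provides frequencies for categorical measures, so a proportion cleared could be shown beside the time. That also stands, but the plan does not tie the two together. A cleared-only time shown with a percentage is still not the time for the whole group.

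Third, the size is assumed. The only document-based input, 15% drop-out, produces little bias by itself, as the 0% rows show. Nothing in the documents indicates that 10% to 30% of subjects would remain uncleared at 24 months, and the event is the investigator's clearance, not actual return. This stands in full and limits what can be claimed.

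Last, the outcome carries no hypothesis or success criterion, and the only historical figures supplied are fusion rates (12.2). That bears on importance, not on correctness.

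**Conclusion.** The point holds as a gap in a descriptive secondary outcome. Time to clearance is right-censored, section 12 has no method for that, and the only numerical summary on offer would by default rest on cleared subjects and understate the time.

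The direction does not depend on the distribution assumed; the size does depend on the share never cleared, which is unknown. Under the exponential assumption the median is understated by 0.2 months if everyone would eventually be cleared, and by 0.9, 1.9 or 3.4 months at 10%, 20% or 30% never cleared. If almost all subjects are cleared, the matter is minor.

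Two stronger readings go beyond the documents. One is that the reported time will be badly wrong; that needs a sizeable never-cleared share, for which they give no evidence. The other is that the study's conclusion is at risk. The fusion test in 12.5 and the sample size in 12.3 do not use this outcome, and no return-to-work benchmark is given against which a biased figure would be judged.

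**What to change.** Add to 12.7 that time to clearance for work or school will be analysed by Kaplan-Meier from the date of surgery, among subjects working or in school pre-operatively, with censoring at last contact or 24 months. Report the median with its 95% CI, if reached, and the proportion cleared by 3, 6, 12 and 24 months. State how many subjects were outside the at-risk set because they were not working or studying before surgery.

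The cost is a short addition to 12.7 and one standard analysis. Pre-operative status (8.2.1) and release at follow-up (8.4.1) are already listed for collection, so no new assessment should be needed. The case report forms are not in the text reviewed, so the sponsor should confirm that they record the clearance date and separate not cleared from not applicable. The reported time may be less favourable than a cleared-only figure. Kaplan-Meier also assumes that drop-out is unrelated to the prospect of clearance, so the number censored before 24 months should be shown.

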5.3.11 Use of Narcotics Post-Surgery

The types and dosages of any narcotics taken by the patient post-surgery will be documented.

6 STUDY ENDPOINT

6.1 Primary Study Endpoint

The endpoint of this study is the fusion status at 24 months.

7 STUDY POPULATION

7.1 Sample Size

A total of two-hundred four (204) total subjects at up to 15 clinical sites, geographically distributed throughout the US, will be enrolled.

7.2 Inclusion and Exclusion Criteria

To be eligible to participate in the study, a subject must meet all of the Inclusion Criteria and none of the Exclusion Criteria.

Inclusion Criteria

1. Diagnosis of spinal stenosis; spondylolisthesis (grade 1 or 2); and/or degenerative disc disease (DDD) with one or two contiguous levels requiring fusion and adjunctive posterior stabilization between L1-S1. Qualified patients will be confirmed for inclusion by patient history and radiographic studies
2. Willing and able to comply with the requirements of the protocol including follow-up requirements
3. Willing and able to sign a study specific informed consent
4. Skeletally mature and ≥ 18 years old at time of enrollment

Exclusion Criteria

1. Previous spine surgery at the index level

(This is not intended to exclude previous microdiscectomies, microlaminotomies and other procedures that do not violate the disc space or that have not destabilized the spine, see also #2.)

2. Previous posterior spine surgery (e.g., posterior decompression) that destabilizes the lumbar spine

(Previous posterior spine surgery is intended to exclude destabilization at the target levels for the EVEREST surgical procedure. For example, previous laminectomies at the index levels will be excluded.)

3. Active systemic infection or infection at the operative site

4. Co-morbid medical conditions of the spine or upper/lower extremities that may affect the lumbar spine neurological and/or pain assessment

5. Metabolic bone disease such as osteoporosis and osteopenia that contraindicates spinal surgery

6. History of an osteoporotic fracture

7. History of an endocrine or metabolic disorder (e.g., Paget's disease) known to affect bone and mineral metabolism

8. Taking medications that may interfere with bony/soft tissue healing including chronic steroid use

(Chronic steroid use is defined as any oral/systemic steroid use (this does not include inhaled, nasal, or topical steroids) for greater than 6 contiguous weeks within 3 months of the date of surgery; and /or >5 mg per day of oral steroids used daily within 2 weeks of the date of surgery.)

9. Known allergy to titanium or cobalt chrome

10. Rheumatoid arthritis or other autoimmune disease or a systemic disorder such as HIV, active hepatitis B or C, or fibromyalgia

11. Insulin-dependent type 1 or type 2 diabetes

12. Medical condition (e.g., unstable cardiac disease, cancer) that may result in patient death or have an effect on outcomes prior to study completion
13. Pregnant, or intends to become pregnant, during the course of the study
14. Severe obesity (Body Mass Index > 40)
15. Physical or mental condition (e.g., psychiatric disorder, senile dementia, Alzheimer's disease, alcohol or drug addiction) that would interfere with patient self-assessment of function, pain, or quality of life.
16. Involved in current or pending spinal litigation where permanent disability benefits are being sought
17. Incarcerated at the time of study enrollment
18. Current participation in an investigational study that may impact study outcomes

7.3 Study Duration

Study subjects will be expected to participate in this study for 24 months following surgery, with follow-up evaluations at initial post-op, 3 months, 6 months, 12 months, and 24 months.

8 STUDY ENROLLMENT/EVALUATIONS

8.1 Patient Screening and Enrollment

Consecutive patients who potentially meet the study inclusion and exclusion criteria will be screened for eligibility. The screening process will be as follows:

- Consecutive patients are potentially eligible for entry into the study based on their age and whether their medical condition appears to generally fit the characteristics specific to this study.
- Patients who agree to enter the study must sign the approved informed consent form.
- A patient is considered enrolled in the study after signing the IRB approved informed consent. Consented patients complete the remainder of the screening process to confirm study eligibility. Patients who do not fulfill the screening criteria are considered Screening Failures and will be documented on the Screening and Enrollment Log. Screening failures will not count against the total number of subjects eligible for analysis.
- Diagnostic imaging studies (standing x-rays) MUST be completed within 180 days of the planned surgery. For diagnostic purposes, an optional pre-op MRI may also be done, per surgeon's standard of care, but does not serve as a substitute for standing x-rays.
- Subject self-assessment questionnaires must be completed within 90 days of the planned date of surgery.
- Subjects who have signed the informed consent and fulfilled the Inclusion/Exclusion criteria are then scheduled for surgery.
- If study surgery is unable to be completed within 90 days of the date of screening, the patient self-assessment questionnaires must be repeated and the site must assess whether any imaging studies need to be repeated (these must be dated within 180 days of surgery). If any imaging study is outside the screening window and has to be repeated, the subject must be exited from the study, re-consented, and assigned a new Subject ID number for re-screening. The Screening Log will provide a means to identify the original Subject ID number for any subjects who are rescreened.

If, after qualifying for the study and before surgery, the subject experiences a significant change in his/her clinical presentation, the changes should be noted in the source documents and any screening tests and imaging repeated if medically indicated. The patient self-assessment questionnaires must be repeated. This subject need not be re-consented to continue the study if any repeated tests are medically indicated. The subject needs not be exited from the study unless the Investigator believes it is in the subject's best medical interest to do so or that the subject no longer meets the eligibility criteria for the study. The following should be considered when evaluating whether or not the change in clinical presentation is considered significant: an increase in related pain of approximately 3 points (on VAS scale from 0-10), a change in the location of the pain, deteriorating neurological status or other conditions where repeat radiographic studies may be necessary. The objective is to ensure that the patient still meets the eligibility criteria based on the medical judgment of the surgeon.

The Subject ID number will be used to capture de-identified information. For this study, the following standardized format will be used: *Site Identifying Number (2 digits)-Subject Identifying Number (3 digits)*. Your site identifying number will be assigned by the Sponsor, and the subject identifying number should start with 001 and continue accordingly during patient enrollment. For example, if the site identifying number issued to you is Site 03, and you are enrolling your second patient into the study, their Subject ID would be 03-002. A Patient Information Log will be provided to you to keep as a cross reference for study subjects.

